Risk: The risk to patients using BFR is anticipated to be minimal overall. Several studies on adults after ACLR has shown that BFR is well tolerated, and our recently published study on BFR in adolescent showed similar findings. ⁵⁷⁻⁵⁹ To monitor patient tolerance, patients will rate pain levels using a visual analog scale,⁶⁰ RPE, and our team will screen for adverse responses. Though these response are rare, we will monitor for pain, bruising, dizziness, and nausea. At subsequent follow up PT visits, we will monitor for any potential delayed events.

Use of results of study

The results of this study would provide the Connecticut Children's Sports Medicine surgeons and physical therapists here at Connecticut Children's information to determine the effectiveness and application of the use of BFR in conjunction with exercise.

Study Budget

Equipment and Supplies: There will be no equipment costs associated with this study. The BFR Delfi units that are necessary for completion of BFR exercise by the intervention group are already owned by Connecticut Children's Sports Physical Therapy

Travel: There will be no travel costs associated with this study.

All personnel will provide effort that is in kind, and there will be no stipends provided to the patients. These follow up assessment visits currently already occur as the standard of care for all patients undergoing ACLR at Connecticut Children's

Budget Justification

All treatment visits and follow up visits will be covered by patient insurance 97110 and 97140 CPT code will cover the costs of all physical therapist treatment visits.

The 97530 codes will cover all assessment visits (12 weeks, 6 months, and return to play)

Note: The sports physical therapists who will guide the patient in performing the functional assessment skills and follow the standard of care in grading these skills will bill their services to the patient's insurance.

Appendices (as needed)

The attached data collection from in MS excel will serve as a template initially. Upon IRB approval, a full RED cap data base will be built to include all data points mentioned above.

CITATIONS:

- 1. Hewett TE SJS, L.Y G. Understanding and preventing noncontact ACL injuries. *Human Kinetics Publishers.* 2007.

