Hypothesis 1b: We hypothesize that isokinetic knee extension peak torque and limb symmetry will be greater in the BFRT group compared to the control group at 6 months and time of return to sport after ACLR. Hypothesis 1c: We hypothesize that the BFRT group will show a greater change in strength from pre-operative testing to 8 weeks post-operative from the control group.

Primary Aim 2: Determine if BFRT during ACLR post-surgical rehabilitation improves patient-reported outcomes (IKDC, KOOS, ACL-RSI) compared to the control group. We hypothesize that the BFRT group will show greater self-reported function and confidence as compared to the control group at all study time points.

Secondary Aim 1: Determine if the use of BFRT during ACLR post-surgical rehabilitation increases mid-thigh

circumference when compared to a control group. We hypothesize that the BFRT group will demonstrate five percent or greater difference in mid-thigh circumference than the control at all study time points.

OUTCOMES DEFINITIONS / DATA POINTS COLLECTED

1) Demographic information:

_		
	a. Age	h. Surgeon
	b. Medical record number	i. Sport
	c. Date of ACL surgery and related surgeries	j. Level of competition in sport
	d. Date of Injury	k. Weight, Height and BMI
	e. Sex	I. Race
	f. Graft Type	m. Insurance status (Public/Private)
	g. Concomitant pathology/Meniscal tear type, laterality	n. Weight bearing status (number of weeks)
	h. Surgeon	

Primary Outcomes Definitions

Active knee range of motion: Knee AROM will be measured in supine position using a goniometer and standardized procedures reported by Norkin and White.³⁵

Mid-thigh circumference will be used to measure and track muscle hypertrophy.

10 Repetition Max Test: The 10 repetition max test will be used to determine an estimate 1 rep maximum on the Shuttle Leg Press machine, as this is a safe and reliable alternative to predicting a 1 rep maximum.

Isometric thigh strength: Preoperative, 8 week and 12 weeks, 6 months and return to play assessments will measure maximum isometric muscle torque using an isokinetic dynamometer (Humac CSMi USA, Stoughton, MA, USA). Return to play assessments will occur at approximately 9 months post-operative.

Isokinetic thigh strength: For assessments at 6 months and time of return to play, maximum muscle torque will be assessed using an isokinetic dynamometer (Humac CSMi USA, Stoughton, MA, USA).

Patient Reported Outcomes:

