Once identified as a potential candidate, the study purpose and protocol will be explained and a brief summary of the study will be provided at the conclusion of the pre-operative appointment. Patients must meet all the requirements of inclusion and exclusion criteria to be eligible for consent.

Consent: Consenting will take place at the pre-operative visit. The patient/parent will be given a detailed description of the purpose and methodology for this study. They will have the opportunity to read the consent forms and ask any questions they may have about the research. If they agree to participate, they will be asked to sign the consent form and a copy will be provided to the patient and family. All consenting documents will be stored in REDCap

If patients agree to enroll, all demographics and information listed in the protocol will be stored in REDCap on a data collection sheet that is listed in the attachments. This sheet will be used to record all pertinent information for all active participants on the study and will be stored in REDCap

Retention: Eligible patients will be required to be seen for a minimum of 80% of patient visits to be included in this study.

Data Collection:

Prior to completing enrollment measures, patients will provide written informed consent to participate in the study. Data collection will occur at five different time points during the rehabilitation process: preoperatively, 8 weeks, 12 weeks, 6 months, and time of return to play. Return to play assessments will be completed at approximately 9 months post-operatively. The schedule of study assessments is listed in Table 1 below.

Table 1. Schedule of Study Procedures and Assessments						
Procedure	Pre-operative	8	12	6	Return	2 year
	Screen	weeks	weeks	months	to Play	follow-up
Informed Consent	x					
Background Information	x					
Patient Reported Outcomes	x	Х	х	х	х	x
Estimated 1 rep Max	X					
Mid-thigh circumference	X	х	Х	х	х	
Isometric thigh strength	X	Х	х	х	Х	
Isokinetic thigh strength				х	х	
Range of motion (ROM)	X	X***	х	х	х	
***ROM will be assessed and collected at each treatment visit for the first 8 weeks after surgery						

Primary Outcomes (See table below):

Active knee range of motion: Knee AROM will be measured in supine position using a goniometer and standardized procedures reported by Norkin and White.³⁵

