- 1. Control Group: All control group participants will follow the ACL reconstruction rehabilitation protocol These patients will complete outcome measures, and standardized strength assessments consistent with the standard current standard of care listed above. The same data points will be collected.
- 2. All data collected all time points will be stored in a custom built REDcap database built specifically for this study.

Recruitment and Retention: We will track recruitment and retention as outcomes. Connecticut Children's sports medicine surgeons and physical therapists care for approximately 100-150 ACL tears per year on average. Our expertise in pediatric sports medicine positions us well to treat these patients after ACLR. Our physical therapists will care for approximately half of these patients on an annual basis. In our recent pilot study, we enrolled approximately 40 patients and had 0% attrition in our BFRT group throughout the study period. Our close relationship and adjoined clinic with our sports medicine providers allows us to target and recruit potential patients for enrollment. Our team has been able to identify and establish formal procedures for the recruitment and consenting process. We anticipate to enroll 2-4 patients/month, and at this rate we would finish enrollment within approximately 10 months.

Study Procedures: All patients that undergo ACLR at Connecticut Children's begin physical therapy within 5-7 days of surgery. The implementation of BFRT will begin at the **second** post-operative visit to account for differences in post-operative pain and recovery.

BFRT Intervention Group:

In addition to the standard ACL rehabilitation protocol, the experimental group will complete 2 exercises using the Delfi BFR cuff 2x/week for 8 weeks during their treatment session at Connecticut Children's Sports Physical Therapy on the second post-operative visit. Exercise selection is listed in Table 2. All patients will use the Delfi BFR unit and will complete exercises at 80% limb occlusion pressure. Cuff size will be determined by patient thigh circumference as described in Delfi BFR unit manual. Limb occlusion pressure will be determined in supine position and all exercises will be completed at 80% occlusion.

Control Group: In addition to the standard ACL rehabilitation protocol, the control group will complete the same exercises as the experimental group starting on the second post-operative visit.

Table 2. Exercise Progre	ession	

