Data will be collected on all patients enrolled into the study. Descriptive statistics will be generated on the demographic characteristics of both treatment groups. We will use a two-way repeated measures analysis of variance to determine the effect of treatment groups, BFRT compared to standard of care therapy, over time on subjective and objective outcomes. Exact analysis for each test will depend on variance and distribution/normality of data set. This will be achieved using the Statistical Package for the Social Sciences (SPSS) software version 27.0 (IBM Corp., Armonk, NY, USA). We will address each aim in the following manner.

Accrual and Expected Duration of Accrual

Once approved, we expect that this study can be accomplished within two to three years. The open period for this study will be between February 2022 and February 2025.

Study Limitations:

There are several limitations anticipated with this study that will impact its power and external validity. These limitations include an inherent sampling bias with our recruitment strategy, lack of patient or participant blinding, and small sample size.

Attempts will be made to reduce any potential bias by having standardized educational scripts regarding BFR training that each treating therapist will read to subjects prior to their first BFR session.

Subjects in our study will likely come from the same surgeons and the same type of ACL graft (QT). This could be a potential limitation in the generalizability of our results to other surgeons and graft types.

Administrative Organization

Roles and responsibilities:

[name], PT, DPT: Will serve as the study's primary investigator. [name] will provide primary support for the SRC and IRB study protocol development and submission, as well as maintaining updates and compliance with clinicaltrials.gov. He will review the required databases and pull the relevant data required to complete this study. He will also aid in data interpretation and manuscript preparation.

All MDs listed: The MDs listed on this proposal will be responsible for recruitment of patients, data interpretation and manuscript preparation.

All physical therapists listed: The PT's listed on this proposal will serve as the study's co-investigator. They will provide support in development of SRC and IRB documents (review of literature). They will help with data collection, recruitment, consenting patients.

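### Secondary Aim 1 hypothesises a 5% circumference difference at every visit, including the pre-operative one that BFRT cannot affect, and the stated ANOVA tests zero, not 5%

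*Protocol*

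**What the plan says.** Under Purpose of the Research, Aims and Hypotheses, the Protocol gives Secondary Aim 1 as a directional question: "Determine if the use of BFRT during ACLR post-surgical rehabilitation increases mid-thigh" circumference compared with control. The hypothesis attached to it adds a size and a scope: a "five percent or greater difference in mid-thigh circumference than the control at all study time points".

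The Data Collection section defines the time points as "five different time points during the rehabilitation process: preoperatively, 8 weeks, 12 weeks, 6 months, and time of return to play". Table 1 has a row for "Mid-thigh circumference" marked at each of these five visits and not at the 2-year follow-up.

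Under Study Procedures, "The implementation of BFRT will begin at the" second post-operative visit, so the pre-operative measurement comes before any BFRT.

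Under Data analysis: "We will use a two-way repeated measures analysis of variance to determine the effect of treatment groups" over time on the subjective and objective outcomes. The section adds: "Exact analysis for each test will depend on variance and distribution/normality of data set". It then says "We will address each aim in the following manner", but the text moves to accrual. Nothing in the section refers to a 5% threshold.

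**The concern.** Two stated elements do not fit the hypothesis.

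- **The visits.** Read as written, the hypothesis requires a 5% difference before treatment begins. Randomisation makes the expected difference there zero, so the hypothesis can hold in full only through chance imbalance. Elsewhere the same section avoids this: Hypotheses 1a and 1b name post-operative visits, and 1c uses the pre-operative value as the baseline for change.
- **The threshold.** The null hypotheses of the ANOVA are no group effect, no time effect and no interaction. None involves 5%, so a significant F test leaves open whether the difference is 5% or something smaller. What the 5% is a percentage of is also undefined. It could be the control mean, the change from pre-op or the uninvolved limb.

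At stake is how the hypertrophy result is worded, and whether the model uses the pre-operative measurement well. As an outcome level it pulls the group main effect towards zero. As a covariate it would remove body-size variation from that effect.

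**Working it through.** **The plan's own figure.** The only sample-size calculation concerns isometric strength: alpha 0.05, power 0.80, effect size 0.6, total N 14, raised to 40. With f = 0.6, two time points and between-visit correlation 0, the noncentrality is 0.6² × 14 × 2 = 10.08 on 1 and 12 df, giving power 0.83, so 14 reproduces. The time-point count and correlation are my inputs; the Protocol does not state them. The figure has no bearing on circumference.

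**Inputs.** From the Protocol: 20 per arm, five visits, 5%. The Protocol gives no mean, SD or correlation for circumference. I assume either a CV of 4-12%, or a mean of 45-52 cm with SD 4-5 cm and a correlation r of 0.8-0.9 between visits.

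**1. The pre-operative visit.** SE of the difference = CV × √(2/20). The true difference is 0.

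| CV | SE | Chance of observing ≥5% favouring BFRT |
|---|---|---|
| 4% | 1.26% | <0.1% |
| 6% | 1.90% | 0.4% |
| 8% | 2.53% | 2.4% |
| 12% | 3.79% | 9.4% |

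To isolate the effect of this visit, suppose a true post-operative difference of 7.5%, CV 4% and between-visit correlation 0.9. The observed difference is at least 5% at all four post-operative visits with probability 0.95. Adding pre-op takes that to about zero. Over CVs of 4, 8 and 12%, correlations of 0.5-0.9 and true differences of 5% or 7.5%, the five-visit probability never exceeds about 9%.

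**2. Significance is not 5%.** For an unadjusted comparison at one visit, the smallest observed difference significant against zero is t(0.975, 38) × SE. That is 2.6% at CV 4%, 3.8% at CV 6%, 5.1% at CV 8% and 7.7% at CV 12%. At the lower CVs, a difference well under 5% is significant. At CV 12%, an observed 6% is not.

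**3. Dilution of the group main effect.** If the difference is 0 at pre-op and 5% at each of four later visits, the five-visit average is (0 + 4 × 5)/5 = 4%.

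**4. Precision of the possible contrasts.** The unadjusted 95% half-width at one visit is 2.024 × SD × √(2/20), or 2.56-3.20 cm. Each other contrast multiplies this by a factor, and the result is divided by 45-52 cm.

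| Contrast | Factor | Half-width, % of mean |
|---|---|---|
| One visit, unadjusted | 1 | 4.9-7.1 |
| Group main effect over five visits | √((1+4r)/5) = 0.917-0.959 | 4.5-6.8 |
| Change from pre-op to one visit | √(2(1−r)) = 0.632-0.447 | 2.2-4.5 |
| One visit, adjusted for pre-op | √(1−r²) = 0.600-0.436 | 2.1-4.3 |

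For the main effect, the extremes are 2.56 × 0.917/52 = 4.5% and 3.20 × 0.959/45 = 6.8%. These exceed the diluted 4% effect throughout the assumed range. The change contrast and the covariate-adjusted contrast are nearly equal.

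**5. What the 5% refers to.** Taken on the circumference itself, 5% of 45-52 cm is 2.25-2.60 cm. Taken on the change from pre-op, it would be a far smaller quantity.

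**The case against.** The strongest reply is that 5% is an expected size and not a decision rule. It appears only in the hypothesis. The aim asks whether circumference increases, and a test against zero answers that. This stands. A reader might infer that the investigators intend to report a significant F test as proof of 5% or more, but the Protocol nowhere says so. Nor is the ANOVA incapable of informing the 5% question, since an interval from the same model could be set against 5%.

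A second reply is that body size does not swamp the stated analysis. This also stands for the group-by-time interaction, which works on within-patient change. The covariate gains little over the change contrast (2.1-4.3% against 2.2-4.5%). Only the group main effect remains exposed.

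Third, including pre-op may be a slip, because the aim concerns post-surgical rehabilitation. That is plausible, but the visit list and Table 1 make the literal reading the natural one. Primary Aim 2 uses the same phrase for patient-reported outcomes.

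Fourth, contrasts and interval rules are commonly left to a SAP, which may exist. Their absence here is therefore not the finding. A SAP could not, however, make a pre-operative BFRT effect possible.

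It is tempting to require a lower confidence limit of at least 5%. The directional aim does not call for that. At one visit, unadjusted, it would need an observed difference of 7.6-12.7% over the assumed CVs, and would succeed only 2.5% of the time if the true difference were exactly 5%.

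**Conclusion.** The point holds in a limited form. The hypothesis is wrongly specified at the pre-operative visit, where 5% favouring BFRT can arise only by chance. The 5% is neither defined nor tested by the stated ANOVA, so significance alone would not show it. Keeping pre-op as an outcome level reduces a constant 5% effect to 4% in the group main effect and leaves that effect exposed to body size.

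The document does not support saying that the aim is untestable or that the whole analysis is too imprecise. The unattainable visit and the 5%-to-4% averaging follow from the Protocol and simple arithmetic. Every probability and half-width rests on an assumed mean, SD, CV or correlation. The importance is minor to moderate: Study Design makes circumference a secondary outcome, although it also appears under the primary outcome definitions.

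**What to change.** 1. Restrict the Secondary Aim 1 hypothesis to 8 weeks, 12 weeks, 6 months and return to play. Check the same phrase in Primary Aim 2.
2. Analyse post-operative involved-limb circumference with its pre-operative value as a covariate, not as an outcome level. Dropping the pre-op level without the covariate would leave body size in the comparison.
3. State what the 5% is a percentage of.
4. Report the adjusted percentage difference with a 95% CI.
5. Base the conclusion on the difference from zero. Describe 5% as the expected size, not as something a significant F test shows.

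The cost is a few lines of wording and one covariate already collected at the pre-operative visit. No added visits or patients are needed. The gain lies mainly in a hypothesis that can be met and a conclusion that follows from the test.

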Level I Sports (4-7 days/week)	Jumping, hard pivoting, cutting (basketball, volleyball,	
	football, soccer, gymnastics, skiing. wrestling)	
	Running, twisting, turning (racquet sports, baseball, hockey)	
Level II sports (1-3 days/week)	() Jumping, hard pivoting, cutting (basketball, volleyball,	
	football, soccer, gymnastics, skiing. wrestling)	
	Running, twisting, turning (racquet sports, baseball, hockey)	

2) Completion of postoperative rehabilitation following standard protocols

3) Orthopedic surgical intervention and physical therapy completed at Connecticut Children's.

Study Group and Control Group Exclusion Criteria

1) An additional lower extremity injury at time of knee injury or previous surgical intervention on the knee (ipsilateral and contralateral)

2) Multiple ligament ruptures or trauma

3) Weight bearing restrictions for greater than 4 weeks after surgery due to concomitant pathology such as meniscal root/radial repair, chondral pathology, or multi-ligament pathology

4) Follow-up surgical procedures including, but not limited to, post-operative arthrofibrosis

6) Inability to attend regular physical therapy sessions (≥80% of patient treatment sessions and all assessment visits

7) Contraindications to performing BFRT including known history of central or peripheral neurologic impairments, cardiac or metabolic condition or history of deep vein thrombosis (DVT).

The exclusion of age is to ensure that the study population is old enough to complete testing on the HUMAC isokinetic dynamometer and young enough to be treated by one of our Sports Medicine physicians.

The secondary diagnosis and previous knee injury exclusions are to limit the influence of other diagnoses or injuries on measured knee strength, as well as provide a more homogeneous group for comparison to past data.

Identification, recruitment, consent and retention of subjects

Patient Screening and Determination of Eligibility

Pre-Screening

All potential patients undergoing ACL reconstruction at Connecticut Children's Sports Medicine will be approached for participation for this study. Patients scheduled to undergo ACL reconstruction will be screened by the individuals listed on this protocol using our pre-screening documentation form. All patients undergoing ACL reconstruction undergo a pre-operative appointment.

Identification and Recruitment:

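### Several eligibility rules, including 80% attendance, depend on events after allocation and, applied as written, remove randomised patients

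*Protocol*

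**What the plan says.** All references are to the protocol.

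- **Timing of eligibility.** Under Identification and Recruitment: "Patients must meet all the requirements of inclusion and exclusion criteria to be eligible for consent". Under Consent: "Consenting will take place at the pre-operative visit".
- **Inclusion criterion 2:** "Completion of postoperative rehabilitation following standard protocols".
- **Inclusion criterion 3:** "Orthopedic surgical intervention and physical therapy completed at Connecticut" Children's.
- **Exclusion criterion 4:** "Follow-up surgical procedures including, but not limited to, post-operative arthrofibrosis".
- **Exclusion criterion 6:** "Inability to attend regular physical therapy sessions", with 80% of treatment sessions and all assessment visits given as the standard.
- **Retention paragraph:** "Eligible patients will be required to be seen for a minimum of 80% of patient visits to be included in this study".
- **Recruitment and Retention paragraph:** "We will track recruitment and retention as outcomes".
- **Data analysis section:** data are to be collected on every enrolled patient. The section does not say that every randomised patient is analysed as allocated.

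The time of randomisation is not given. Under Study Procedures, both arms start the study exercises at the second post-operative visit, with the cuff in one arm and without it in the other.

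**The concern.** An eligibility rule protects a randomised comparison only if it can be settled before allocation. A rule that depends on what happens later selects among patients already randomised, and what happens later may depend on the arm. The retained groups are then no longer the groups that randomisation made comparable.

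Here the arms are not blinded (Study Limitations), so attendance and dropping out can differ by arm. Exclusion 4 also selects on something close to an outcome: it names arthrofibrosis, which limits knee motion, and knee range of motion is listed under the primary outcomes. Excluding re-operated patients can also keep re-operations out of the results, and re-operation is not among the events that the Risk paragraph names for monitoring.

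At stake is every between-group comparison in the trial. If follow-up of removed patients stops, later analysis cannot recover it.

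**Working it through.** **1. When each rule can be judged.** Allocation must be known by the second post-operative visit at the latest, because the arms differ from then on.

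| Rule | Known at pre-operative consent? | Known by second post-operative visit? |
|---|---|---|
| Inclusion 2, rehabilitation completed | No | No |
| Inclusion 3, therapy completed at the centre | No, as worded | No, as worded |
| Exclusion 4, follow-up surgery | No | Not in general |
| Exclusion 6, inability to attend | Yes, as a screening judgement | Yes |
| Retention, seen for at least 80% of visits | No | No |

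Exclusion 4 cannot be a rule about earlier operations, since exclusion 1 already covers previous knee surgery. The Retention sentence cannot be a screening judgement: it applies to patients who are already eligible and turns on visits attended, not on ability to attend.

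**2. How easily the 80% line is crossed.** The protocol does not define the denominator. If it were the BFRT-period sessions, 2 per week for 8 weeks gives 16. Missing 3 leaves 13/16 = 81%; missing 4 leaves 12/16 = 75%, which fails.

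**3. Size of a possible bias.** The plan has no figure of its own here. It states no expected removal rate, and its only attrition figure is 0% in the pilot's BFRT group. The one input from the plan is 20 per group. Assumed: no true effect, one time point, outcome in SD units, correlation r between adherence and outcome, and removal of the least adherent patients.

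The mean adherence of 20 standard normal values after dropping the lowest 1, 2 or 4 is 0.098, 0.182 or 0.333. Then

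shift = r × (difference between arms in mean retained adherence).

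For example, 4 removed from BFRT and none from control at r = 0.7 gives 0.7 × 0.333 = 0.23 SD. For 4 against 2 at r = 0.5 it is 0.5 × (0.333 − 0.182) = 0.08 SD. Rejection rates come from 40,000 simulated trials with a two-sided two-sample t test at 5%.

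| Removed, BFRT v control | Shift in SD at r = 0.3 / 0.5 / 0.7 | Rejection rate, % |
|---|---|---|
| 2 v 0 | 0.05 / 0.09 / 0.13 | 5.4 / 6.1 / 7.2 |
| 4 v 0 | 0.10 / 0.17 / 0.23 | 6.1 / 8.1 / 11.5 |
| 2 v 1 | 0.03 / 0.04 / 0.06 | 5.1 / 5.8 / 6.4 |
| 4 v 2 | 0.05 / 0.08 / 0.11 | 5.4 / 6.1 / 7.6 |
| 2 v 2 or 4 v 4, same selection | 0 | about 5 |

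The sign reverses if the removals fall on the control arm. Equal removal costs only precision: the standard error grows by √(20/18) = 1.05 or √(20/16) = 1.12.

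**4. Separate check.** A second simulation (20,000 trials, r = 0.5) removed patients below a threshold set to drop 20% on average. Removal from BFRT only gave +0.175 SD and 7.9% rejection; from control only, −0.175 SD and 8.2%. Removal unrelated to outcome, or identical in both arms, gave no bias. Removal of 20% in both arms with opposite selection gave 0.35 SD and 17%.

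**5. Change from baseline.** Hypothesis 1c concerns change from pre-operative testing. In units of the single-time-point SD, the shift is (correlation of adherence with later strength − correlation with pre-operative strength) × the same difference in retained adherence. It is zero if the two correlations are equal. If they are 0 with pre-operative and 0.5 to 0.7 with later strength, it is 0.09 to 0.13 SD for 2 v 0 and 0.17 to 0.23 SD for 4 v 0.

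**The case against.** The strongest reply is that some of this is loose wording. The Study Design section describes patients who will have their surgery and therapy at the institution, so inclusion 3 can be meant as a site restriction and inclusion 2 as the expected care pathway. That is a fair guess at intent, and it is why rewording is enough for inclusion 3. It does not rescue the Retention sentence or exclusion 4.

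Nor does the protocol say outright that a removed patient's data are dropped from the analysis. Data are collected on all enrolled patients, so an SAP, which is not at hand, could define an all-randomised set. It could, but it would then analyse patients whom the protocol says are not in the study. Tracking retention as an outcome can be squared with an 80% threshold, but not easily with making that threshold a condition of inclusion.

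The size of the bias is assumed, and the milder cases are small: 2 v 1 barely moves the error rate. The pilot saw no attrition in its BFRT group. Both arms do the same exercises, and reduced tolerance of the cuff stops an exercise, not a visit. All of this stands and limits what can be claimed about size. But the pilot figure covers one arm, and it says nothing about attendance below 80% or re-operation.

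Finally, the demographic data list includes related surgeries. That entry might capture re-operations, or it may mean procedures done with the reconstruction, so the point on unreported re-operations is a possibility only.

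**Conclusion.** The concern holds. The protocol requires all criteria to be satisfied before consent, yet inclusion 2, inclusion 3 as worded, exclusion 4 and the Retention sentence depend on later events. Whenever randomisation takes place up to the second post-operative visit, these rules take effect by removing randomised patients.

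Bias is possible, not certain, and can go either way. Under the assumed correlations of 0.3 to 0.7, one-sided removal of 2 to 4 of 20 patients shifts the difference by 0.05 to 0.23 SD and raises a 5% error rate to between 5 and 12%. Unequal removal in both arms (2 v 1 or 4 v 2) gives 0.03 to 0.11 SD, and equal, similarly selected removal gives none. The removal rates and correlations are assumptions; the timing conflict does not depend on them. It should be corrected because it affects every comparison.

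**What to change.** 1. Limit eligibility to facts known before allocation, and state when randomisation takes place.
2. Delete inclusion 2, exclusion 4 and the Retention sentence as conditions of being in the study.
3. Reword inclusion 3 and exclusion 6 as baseline expectations: surgery and therapy are planned at the centre, and the patient expects to be able to attend.
4. State that the main analysis includes all randomised patients in their allocated group, including those re-operated or seen for under 80% of visits.
5. Use the 80% threshold only for a labelled, supportive per-protocol analysis, with its denominator defined.
6. Report attendance and re-operations by arm.

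The change is to protocol wording and adds no assessment. It still takes effort, since outcomes must be sought from patients who attend poorly or are re-operated. The estimated effect may also be slightly smaller because non-adherent patients stay in.
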